Title:

Uncemented Hemiarthroplasty, Radiological features comparing Lateral versus Anterolateral approach: A follow-up of a randomized controlled trial.

Study Protocol

The following protocol is an extension of the project: Surgical treatment of displaced femoral neck fractures in patients between 70 and 90 years. A prospective, randomized study, comparing the lateral approach to the anterior muscle sparing approach.

Project title: Uncemented Hemiarthroplasty, Radiological features comparing Lateral versus Anterolateral approach: A follow-up of a randomized controlled trial.

Hypothesis: There is no difference in component positioning or heterotopic ossification in uncemented hemiarthroplasty operated in lateral (Hardinge) or anterolateral (modified Watson-Jones/Röttinger) approach.

The study's main objective:

To compare leg length, femoral offset, valgus/varus position, canal fill ratio and heterotopic ossification between the two approaches, and to investigate the morphology of the proximal femur with canal flare index, Dorr classification and femoral cortical thickness index. If a difference exists, we will compare the results to existing clinical findings (Harris Hips score, PROM data and Timed Up and Go test).

Background:

In Norway approximately 9,000 persons are operated every year for a fracture of the proximal femur. Of these, 38% are displaced femoral neck fractures(1). The mortality rate is approximately 25% the first year(2-5). Hemiarthroplasty is a universally accepted method for the treatment of displaced femoral neck fractures in patients over 70 years (6, 7). Several studies have compared the posterior approach to either anterior or lateral approach, and dislocation is often the primary outcome(8). Due to the risk of dislocation following the posterior approach, there is increased popularity of the muscle preserving approaches(9). Concerns about component positioning is relevant because for limited exposure(10, 11). In total hip replacement, geometrical restoration of leg length and femoral offset is important for patient satisfaction and postoperative function. These patients often perceives leg length discrepancy of 10mm(12) and a 15% reduction of offset is associated with increased frequency of gate disorders(12). A decrease in femoral offset can cause impaired function in terms of reduced abduction strength(13), induce instability(12) and a limp(14). Valgus/varus position may influence early loosening, especially in cemented stems, the reports on cementless stems is varying (15). Surgical approach is expected to effect the clinical outcome in this fragile population(8). In the current literature, lateral- and anterior approaches have comparable results. The effect of hemiarthroplasties inserted through the muscle preserving approach on femoral neck fractures is still unclear, but may be beneficial in terms of less pain and earlier mobilisation (9, 16-18).

Heterotopic ossification (HO) is a common complication following total hip arthroplasty, the incidence vary widely in the literature(19) and surgical approach is shown to affect the incidence(20). The Brooker classification is the most widely used grading system(21). For most patients the presence of HO is not clinically significant, but it may correlate with limitations in range of motion. Kocic et al found that only higher grades of HO is related to poorer clinical outcome(22). HO is possibly less common in cementless hemiarthroplasty. Corrigan et al found that the overall rates of HO in hemiarthroplasty patients did not vary with the surgical approach, but in patients who develop HO, the anterior and anterolateral approaches is associated with higher ossification rates.

Is there a difference in component positioning or heterotopic ossification in uncemented hemiarthroplasty operated in lateral (Hardinge) or anterolateral (modified Watson-Jones/Röttinger) approach?

In this study we wanted to compare the radiological features and stem positioning in two well described approaches operated by experienced surgeons. Experienced surgeons defined as having done more than 50 arthroplasties for each approach, hopefully minimizing poorer results due to longer learning curve and restricted visibility in the modified Watson-Jones approach (23).

In our study we defined leg length as the perpendicular distance between a horizontal line passing through the lower edge of the teardrop to the ipsilateral center of the femoral head(24).

Femoral offset/Global offset was defined according to Lecerf et al as the distance between the longitudinal axis of the femur to the centre of the femoral head and the distance from the centre of the femoral head to a perpendicular line passing through the medial edge of the teardrop(25).

Valgus/varus position was measured on the AP and lateral view in relation to the femoral axis.

Canal fill ratio was evaluated at the following points; 2 cm above the lower trochanter, at the tip of the lower trochanter, 2 cm and 7 cm below the tip of lesser trochanter(26).

Heterotopic ossification was classified as type 1-4 according to Brooker classification(27).

The proximal femur morphology evaluated by canal flare index(CFI)(28), Dorr classification(29) and cortical thickness index (CTI)(30). CFI defined as the ratio of the intracortical width of the femur at 20 mm proximal to the tip of lesser trochanter and isthmus at 10 cm distally. CTI defined as the ratio of cortical width minus endosteal width, to cortical width at 10 cm below the tip of lesser trochanter.

Two of the authors blinded to the surgical approach do the radiological measurement.

Primary outcome:

Leg length

Secondary outcome:

Femoral offset

Valgus/Varus position

Canal fill ratio

Heterotopic ossification

Canal flare index

Dorr classification

Cortical thickness index

Radiographic evaluation:

Included an AP view of the pelvis and lateral view of the hip. The parameters was measured on pre and post operative x-rays, and at 12 months postoperative.

Inclusion/Exclusion criteria:

In addition to the existing criteria defined in the original protocol, we excluded patients with arthroplasty, history of fracture or fracture implants in the contralateral hip.

The handling and analysis of data

The data is entered into the statistical program SPSS (SPSS Inc, Chicago, Illinois).

Sample size and and power calculation:

Based on the sample size and power calculation already done in the primary project. The sample size would be sufficient to detect a mean difference between two groups of approximately half their SD, both continuous and normally distributed outcome variables with a statistical power of 80%.

Statistical method:

Data were examined for normal distribution using histograms, Q-Q plots and the Shapiro-Wilks test. The groups were compared with the Student's independent samples t-test for continuous data, whereas categorical variables were analyzed using Pearson's chi-square test. The Student's paired samples t-test was conducted to compare changes from baseline to follow-ups. The Wilcoxon signed-rank test / Mann-Whitney U-test was performed when the normal distribution- assumptions of the Student's t-test were not met. The strength of the association between primary and secondary continuous outcomes was assessed with the Pearson correlation coefficient. Binary outcomes were assessed using logistic regression or Pearson Chi-Square test. We plan to do an intraclass correlation analysis on the measured results and a Bland-Altman plot. We plan to perform several sensitivity analysis to assess the robustness of our results and possibly do a correction for repeated measurements.

A p-value of < 0.05 was considered statistically significant. We used IBM SPSS Statistics version 25 for Windows. All statistical analysis was conducted using IBM SPSS statistics 21 for Windows (SPSS Inc., Chicago, Illinois).

Ethics

The trial was approved by the regional ethics committee Regional Committees for Medical and Health Research Ethics (REC) and registered with ClinicalTrials.gov. The trial was reported based on the guidelines of the CONSORT Statement(31) and in compliance with the Helsinki Declaration. Informed consent was obtained from all individual participants included in the study.

Publication:

Results will be published in international Orthopaedic journals with referee evaluation.

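### The comparison with clinical function runs only if an undefined radiographic difference appears, and the arms are compared by p-value alone, so a non-significant result could neither support the no-difference hypothesis nor justify skipping that step

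*Combined protocol and SAP*

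**What the plan says.** The Hypothesis is worded as a null: "There is no difference in component positioning or heterotopic ossification in uncemented hemiarthroplasty" between the two approaches. The research question after the Background is neutral: "Is there a difference in component positioning or heterotopic ossification in uncemented hemiarthroplasty".

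The main objective lists five features to be compared between approaches (leg length, femoral offset, valgus/varus position, canal fill ratio, heterotopic ossification) and three measures of femoral morphology. It then adds the conditional step: "If a difference exists, we will compare the results to existing clinical findings". The clinical findings are named in the same sentence as the Harris Hip Score, PROM data and the Timed Up and Go test.

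Leg length is the sole primary outcome. On timing, the Radiographic evaluation section says: "The parameters was measured on pre and post operative x-rays, and at 12 months postoperative".

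Under Statistical method, the between-arm comparison is by Student's "independent samples t-test for continuous data, whereas categorical variables were analyzed using Pearson" (the chi-square test), with Mann-Whitney where normality fails and logistic regression as an option for binary outcomes. The threshold is: "A p-value of < 0.05 was considered statistically significant". The only association analysis is a Pearson correlation between primary and secondary continuous outcomes, and the outcome list contains no clinical score.

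The sample size section gives no N. It refers to the parent project and states: "The sample size would be sufficient to detect a mean difference between two groups of approximately half their SD", with 80% power.

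**The concern.** Two gaps meet here.

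- **The trigger is undefined.** The plan does not say which radiographic outcome must differ, on the postoperative or the 12-month film, or by what size or test. A reader of the report could not tell whether the function comparison was run, or left out, because of what the data showed. Nor does the plan say how the comparison would be done, since the planned correlation does not cover the clinical scores.
- **The arms are compared by significance tests alone.** No interval for the between-arm difference is mentioned, and nothing says how p ≥ 0.05 is to be read. With a hypothesis of no difference and p < 0.05 as the only criterion on offer, a non-significant result could easily be taken as support for the hypothesis and as the reason to omit the function comparison.

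The Background justifies studying leg length and offset by their effect on satisfaction and function. Skipping the clinical step after an inconclusive radiographic result would drop the part that gives the radiographic findings their meaning.

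**Working it through.** **Inputs from the plan:** detectable difference about 0.5 SD, power 80%, significance at p < 0.05. **Assumed, because not stated:** two-sided test, 1:1 allocation, normal outcome with equal SDs.

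**1. Sample size implied by the plan's own claim.** By the normal approximation, n per arm = 2(1.96 + 0.842)² / 0.5² = 62.8, so 63. By the t-test, 63.8, so 64, where power is 80.1%. With no N in the document, the 80% cannot be checked against an actual sample size.

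**2. How often a real difference gives p ≥ 0.05** (noncentral t, 64 per arm):

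| True difference | P(p ≥ 0.05) |
|---|---|
| 0.2 SD | 80% |
| 0.3 SD | 61% |
| 0.4 SD | 39% |
| 0.5 SD | 20% |

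**3. What a non-significant result leaves open.** The 95% interval half-width in SD units is t × √(2/n) = 1.979 × √(2/64) = 0.350. If p ≥ 0.05, the estimate lies within 0.350 SD of zero, so the farther limit lies between 0.35 SD (estimate at zero) and 2 × 0.350 = 0.70 SD (estimate just short of significance). The upper end exceeds the 0.5 SD that the plan sets out to detect.

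**4. Sensitivity for 12-month films.** The Background cites about 25% first-year mortality. If that fraction were missing (an assumption, not the trial's own loss), 64 × 0.75 = 48 per arm. P(p ≥ 0.05) at 0.3 SD becomes 69%, the half-width is 1.986 × √(2/48) = 0.405 SD, and the farther limit runs from 0.41 to 0.81 SD.

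**5. How often the trigger fires with no true difference, if read as p < 0.05.**

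- Leg length alone at one time point: 5%.
- Any of the five compared outcomes, one test each and independent: 1 − 0.95⁵ = 23%.

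The wording does not say which reading applies.

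**The case against.** **The tempting stronger reading.** A reader might infer that the plan treats p ≥ 0.05 as proof of no difference. The documents do not say so. The hypothesis can be an ordinary null, the research question is neutral, and no sentence ties p < 0.05 to the trigger. What can be said is that the plan leaves the reading open and supplies nothing but the p-value to decide it.

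**The clinical outcomes are named.** This is correct. The gap concerns the radiographic trigger and the linking method, not the choice of instruments.

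**Leg length is the natural trigger.** It is the only primary outcome, and on that reading at a single time point false activation is 5%. The higher figure needs a looser reading. But the sentence follows a list of five compared features and does not single out leg length.

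**The parent protocol may hold the details.** It may define the PROM data and clinical time points. It is less likely to define a trigger based on radiographs that belong to this extension.

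**SD units do not show clinical importance.** This stands. The leg-length SD is not given. The Background says total hip patients often perceive a 10 mm discrepancy. The worst-case limit of 0.70 SD reaches 10 mm only if the SD is at least 10/0.70 = 14.3 mm (10/0.81 = 12.3 mm at 48 per arm). With a smaller SD, a non-significant result would exclude 10 mm. That is a reason to report the interval in millimetres, since the p-value cannot show it. The 10 mm figure is not by itself an agreed margin.

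**Ossification cannot be sized here.** It is graded Brooker 1–4. The precision of a risk difference depends on a cut-point and an incidence that the plan does not give, so no figure is offered.

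**An unconditional analysis changes the question.** It asks whether positioning relates to function under either approach, rather than whether a difference between approaches matters clinically. It also brings multiplicity: nine measures (two views for valgus/varus, four levels for canal fill) by three scores is 27 tests, and 1 − 0.95²⁷ = 75% chance of at least one p < 0.05 if independent. This stands, and it is why the fix is limited to a small named set.

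**Conclusion.** The concern holds in a limited form. The trigger for the function comparison is undefined. No between-arm interval is mentioned, and the intraclass correlation and Bland-Altman plot planned on the measurements are not presented as one. No stated method links radiographs to clinical scores. Nothing elsewhere in the document repairs this.

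At the roughly 64 per arm implied by the plan's power claim, a true 0.3 SD difference in leg length would be non-significant about 61% of the time, and every non-significant result leaves at least 0.35 SD, and up to 0.70 SD, inside the 95% interval. So p ≥ 0.05 could not support the hypothesis or justify skipping the function comparison.

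These figures rest on a two-sided 5% level, 1:1 allocation and the stated 80% power at 0.5 SD. The additional contralateral-hip exclusions could reduce the numbers below those of the parent trial. The leg-length test itself is not invalid; what needs repair is its interpretation and the clinical step that follows it. The change should be made.

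**What to change.** **1. Estimates and interpretation.**

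- Report the between-arm difference with a 95% confidence interval for leg length (primary) and the other continuous outcomes.
- Report a risk difference with a 95% interval for ossification, at a Brooker cut-point fixed before analysis.
- State that p ≥ 0.05 alone is inconclusive and does not confirm the hypothesis.
- Claim no relevant difference only against a justified margin fixed before the arms are compared.

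**2. The function comparison.** Do not let significance decide whether it is run. Analyse all patients with existing clinical scores, adjusted for arm. Limit it to a small named set, for example leg length and offset against the named scores at a named time point. Label it exploratory and report estimates with intervals. If the sponsor prefers the conditional question, the minimum is to tie the trigger to a named outcome (leg length is the natural one), film and criterion.

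**Cost.** Wording and a little extra analysis; the clinical findings are described as existing, so no new data are needed. A non-significant result may have to be reported as inconclusive.

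The exploratory analysis has modest power. For a single correlation of 0.25 (Fisher z, two-sided 5%) it is 81% with 128 patients and 69% with 96, if all have scores. Multiplicity remains even in a small set: two measures by three scores is six tests, and 1 − 0.95⁶ = 26% chance of at least one p < 0.05 if independent.

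The Statistical method section mixes past tense with statements of intent. If the arms have already been compared, a margin can no longer be prespecified, but the intervals and the inconclusive wording still apply.

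### Three measures of the patient's own femur are listed as secondary outcomes with no time point; their pre-operative values belong in the baseline description and, if used, as pre-specified covariates

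*Combined protocol and SAP*

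**What the plan says.** The measurement definitions describe the three indices as anatomy: "The proximal femur morphology evaluated by canal flare index(CFI)(28), Dorr classification(29) and cortical thickness index (CTI)(30". Canal flare index is a ratio of two internal canal widths. The third index is defined from the cortex: "CTI defined as the ratio of cortical width minus endosteal width, to cortical width at 10 cm below the tip of lesser trochanter". Neither definition refers to the implant.

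The list headed as secondary outcomes has seven items. The last three are canal flare index, Dorr classification and "cortical thickness index", placed beside femoral offset, valgus/varus position, canal fill ratio and heterotopic ossification.

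The hypothesis is narrower: "There is no difference in component positioning or heterotopic ossification in uncemented hemiarthroplasty operated in lateral (Hardinge) or anterolateral" approach. The main objective likewise compares positioning and ossification between approaches, and then adds a separate clause, "and to investigate the morphology of the proximal femur with canal flare index, Dorr classification and femoral cortical thickness index". It goes on to say that, if a difference is found, the results will be set against the clinical findings. It does not say which differences count.

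On timing, the radiographic evaluation section says only: "The parameters was measured on pre and post operative x-rays, and at 12 months postoperative". No exception is made for the morphology indices.

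On analysis, the statistical method section says: "The groups were compared with the Student's independent samples t-test for continuous data", with chi-square for categorical variables and significance at p < 0.05. Logistic regression is an option for binary outcomes. No covariate is named and no linear model is planned.

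**The concern.** A secondary outcome of a randomised comparison should be something the intervention could change. A pre-operative canal width or cortical thickness is fixed before the incision. A between-arm test on it asks only whether randomisation happened to balance that feature, so a small p-value says nothing about approach. As the plan stands, such a result could be reported as a radiological difference between approaches, and on one reading it could set off the comparison with clinical scores.

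The same indices are plausible predictors of how a stem sits. Canal fill ratio is measured, among other levels, 2 cm above the lesser trochanter, and canal flare index uses the canal width 20 mm proximal to its tip, which is essentially the same level. A pre-specified adjustment could sharpen the comparison of canal fill and alignment at no extra measurement cost, but the plan assigns the indices no such role.

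**Working it through.** **1. The sections side by side.**

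| Section | Role given to morphology |
|---|---|
| Hypothesis | None; positioning and ossification only |
| Main objective | A separate clause: to be investigated |
| Secondary outcome list | Three of seven outcomes |
| Radiographic evaluation | Three time points, no exception |
| Statistical method | Falls under the t-test or chi-square at 0.05; not named as a covariate |

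The outcome list and the test rule do not match the hypothesis and objective.

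**2. What a between-arm difference could mean, by film.**
- Pre-operative: with randomisation intact, chance imbalance only.
- First post-operative: the same bone imaged with the stem in place. A difference would again be mainly chance or measurement.
- 12 months: chance, bone remodelling, or selection through deaths and missing films. The background section gives about 25% first-year mortality for this type of patient. That is a general figure and not this trial's attrition.

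Because the plan names no film for the indices, a reader could not tell these explanations apart.

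**3. Chance findings.** Input: alpha = 0.05 (statistical method section), three tests, no adjustment across outcomes.
- If independent: 1 − 0.95³ = 0.143.
- Under any dependence: between 0.05 (fully overlapping tests) and 3 × 0.05 = 0.15.

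**4. The plan's own power statement.** It claims about 0.5 SD at 80% power and gives no N, so there is no sample size to reproduce. Assuming two-sided alpha and 1:1 allocation, n per arm = 2(1.96 + 0.842)²/0.5² = 62.8, so 63. The t-distribution gives 63.8, so 64. The 64 is implied by the power statement and is not stated in the documents.

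**5. What adjustment might add.** If the covariates together correlate r with the outcome, the residual SD is multiplied by √(1 − r²), so the standardised difference becomes 0.5/√(1 − r²). With 64 per arm and a two-sided t-test:

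| r (assumed) | Variance removed, r² | Standardised difference | Power |
|---|---|---|---|
| 0 | 0% | 0.500 | 80.1% |
| 0.1 | 1% | 0.503 | 80.5% |
| 0.3 | 9% | 0.524 | 83.7% |
| 0.5 | 25% | 0.577 | 90.0% |

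The documents give no value of r. The gain runs from negligible to about 10 percentage points over this range.

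**The case against.** The strongest reply is that the sponsor already keeps morphology apart. The hypothesis leaves it out, the objective only investigates it, and the clinical comparison is most naturally triggered by positioning or ossification. On that reading the outcome list is a loose inventory of what is measured. This is a fair account of intent, and it makes the fault partly one of inconsistency. It does not remove the fault: the indices carry the label of secondary outcomes and the test rule exempts none of them.

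A reader might infer that any between-arm difference in these indices must be chance. The documents do not support that. The definitions fix where on the femur the indices are measured, not when, and the parameters are also measured after surgery and at 12 months. A late cortical thickness index is a post-treatment value that could in principle change, and loss of patients could unbalance the arms.

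A reader might also infer that the value of the indices as covariates is lost. That goes too far as well. The measurements are collected, correlations between leg length and the continuous secondary outcomes are planned, logistic regression is allowed for binary outcomes, and unspecified sensitivity analyses are left open. The original protocol, which this one extends, is not among the documents and may say more. The covariate role is unspecified. However, the planned correlations concern leg length and not canal fill or alignment, and an adjustment chosen after the data are seen carries less weight than one fixed beforehand.

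Finally, an unadjusted comparison in a randomised trial is valid, and adjustment is a matter of efficiency. That stands, and it limits how much weight the power figures can bear.

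**Conclusion.** The point holds in limited form. Three descriptors of the patient's own bone are classed as secondary outcomes and exposed to significance tests, against the plan's own hypothesis, and with no film specified. For pre-operative values these tests cannot show an effect of approach. They carry a 14.3% probability of at least one false difference if independent, and 5% to 15% under any dependence. For 12-month values a difference would be ambiguous between chance, remodelling and selective loss.

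The covariate argument is secondary. Its size rests on an assumed 64 per arm and an assumed correlation, and at r = 0.1 it is worth less than half a percentage point of power. The unadjusted comparison of the primary outcome, leg length, is not affected. This should be corrected, but it does not threaten the trial's main result.

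**What to change.** 1. Remove canal flare index, Dorr classification and cortical thickness index from the secondary outcome list. Report their pre-operative values by arm as baseline characteristics, without p-values.
2. State that these indices do not count towards the difference that triggers the comparison with clinical findings.
3. Compare canal fill ratio and valgus/varus position with a linear model containing arm plus pre-operative canal flare index and cortical thickness index, specified before the analysis.
4. If remodelling is of interest, define the change in cortical thickness index from the first post-operative film to 12 months as a separate exploratory item.
5. If the correlation of the indices with leg length is still wanted, name it explicitly, since it would no longer follow from the outcome list.

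The cost is wording only. The films and measurements are already planned, no patients are added, and the secondary outcome list falls from seven items to four.

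### For femoral offset, a paired change from the pre-operative film measures fracture displacement as well as surgery; the contralateral hip should be the reference

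*Combined protocol and SAP*

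**What the plan says.** The Radiographic evaluation section gives three film times and ties no parameter to any of them: "The parameters was measured on pre and post operative x-rays", and again at 12 months. The films are an AP view of the pelvis and a lateral view of the hip.

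The Statistical method section then states: "The Student's paired samples t-test was conducted to compare changes from baseline to follow-ups". It does not define baseline, list the outcomes tested or exempt any. The non-normal alternative inherits the same gap: "The Wilcoxon signed-rank test / Mann-Whitney U-test was performed when the normal distribution- assumptions" are not met. The comparison of the two approaches is assigned separately, to the "independent samples t-test for continuous data, whereas categorical variables were analyzed using Pearson's chi-square test".

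The parent project, named at the start of the protocol, is "Surgical treatment of displaced femoral neck fractures in patients between 70 and 90 years", so every pre-operative film shows a displaced fracture on the side to be operated. Offset is defined, before the Primary outcome heading, from the longitudinal axis of the femur to the head centre, with a further distance from the head centre to a perpendicular at the teardrop. Leg length is the distance from "a horizontal line passing through the lower edge of the teardrop to the ipsilateral center of the femoral head".

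The Inclusion/Exclusion criteria remove patients whose contralateral hip has an arthroplasty, a past fracture or fracture implants. The plan never says that this hip is measured or used as a reference.

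**The concern.** The Background presents restoration of leg length and offset as what matters to function, and cites a 15% reduction in offset as a level linked to gait problems. Both ideas need a native reference value. The only reference that the analysis section names is an undefined baseline. If that is the injured hip before surgery, the offset reference is distorted by the fracture being treated.

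A significant paired change in offset within an arm could then be reported as restoration, or as alteration by the surgeon, when part or most of it is the displacement disappearing. That happens under either approach. Two within-arm tests also invite the reader to set one p-value against the other, which is not a test of a difference between approaches.

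**Working it through.** No figure in the documents tests this point, so the check sets the statements side by side and reasons from the definitions.

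**Which film is baseline?** The film times are pre-operative, post-operative and 12 months. A pre-operative baseline leaves two later films, which fits the plural in "paired samples t-test was conducted to compare changes from baseline to follow-ups". A post-operative baseline leaves only one. The pre-operative reading is the natural one, though the text does not compel it.

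**What each parameter can give on the pre-operative film of the injured hip:**
- *Femoral offset:* measurable, but its two landmarks (femoral axis and head centre) are separated by the fracture, so the value includes displacement.
- *Valgus/varus position and canal fill:* these describe an implanted stem. There is none before surgery, so no pre-operative value and no paired change from it.
- *Heterotopic ossification:* the Background treats it as a complication following arthroplasty, so a pre-operative grade carries no information.
- *Canal flare index, Dorr class, cortical thickness index:* these describe native bone and can be read pre-operatively.
- *Leg length (primary outcome):* teardrop line to head centre. Both landmarks lie proximal to the fracture, so the distance can be measured but does not register shortening at the fracture.

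**Offset in symbols.** For one patient let N be the native offset, D the amount that displacement adds to or takes from it on the pre-operative film, P the post-operative offset and C the contralateral offset.

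- Paired change: P − (N + D) = (P − N) − D.
- Side difference: P − C = (P − N) + (N − C).

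The quantity of interest is P − N. The paired change is wrong by D, and the within-arm mean change is wrong by the mean of D, one for one. If surgery restored offset perfectly on average (mean of P − N equal to 0), the paired test would still reject, given enough patients, whenever the mean of D is not 0. If the mean of P − N happened to equal the mean of D, it would miss a real alteration. The side difference carries only natural left-right asymmetry, N − C, which the fracture does not enter.

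**Between arms.** Randomisation gives D and N − C the same expected value in both arms. A comparison of P, or of P − C, between arms therefore estimates the difference in P − N without bias from the fracture. D does harm in the within-arm test.

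**Size.** The documents give neither D nor any offset SD, so the error in the paired change cannot be expressed in millimetres or per cent. Nothing in them shows that it is small beside the 15% cited in the Background.

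**The case against.** The strongest reply is that baseline is undefined, so the fault is conditional. First post-operative film to 12 months is an available reading and is sound for stem parameters. A sensible reader would also measure each parameter only where it exists: nobody can compute canal fill without a stem, so that test cannot mislead. And the main objective rests on independent-groups tests, which do not use the paired test.

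Most of this stands, and it rules out three stronger readings that a reader might infer.

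- *That the whole paired analysis is invalid.* The documents do not support this. The morphology indices can be read pre-operatively, a post-operative baseline would serve stem angle and canal fill, and for those two and ossification the gap is one of clarification.
- *That the comparison of approaches is biased.* It is not. The independent-groups tests do not depend on the paired test, and randomisation balances displacement in expectation. The objective turns to clinical findings only if a difference exists, and that difference is sought between the approaches.
- *That the trial loses power.* This would follow only if change scores were compared between arms, which the plan does not describe. With equal SDs the variance ratio of change to post-operative value is 2(1 − ρ), where ρ is the correlation between the pre-operative and post-operative values: a loss below ρ = 0.5, none at 0.5, a gain above it. The documents give neither ρ nor a sample size, so no power figure is justified.

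What the reply does not answer is offset. It can be measured on the injured hip before surgery, the plan does not exempt it from the paired test, and the result would be a number that looks interpretable and is not. The contralateral exclusion hints at a better reference, but no section specifies one.

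**Conclusion.** The concern holds for femoral offset, in a limited form. Under the natural reading of baseline, the paired change mixes the effect of surgery with removal of displacement and cannot show whether native offset was restored or altered. A within-arm test, for offset or any other outcome, does not compare the approaches.

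The reach is one secondary outcome in a supplementary within-patient analysis; the planned between-arm comparison is unaffected. The conclusion rests on two assumptions: that baseline means the pre-operative film of the fractured hip, which the plural follow-ups favour but do not prove, and that displacement changes the distance from femoral axis to head centre, which follows from the position of the landmarks. Using the contralateral hip assumes in turn that left-right asymmetry is modest or at least unrelated to arm; randomisation secures the latter.

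It would be tempting to extend the same remedy to leg length. The definition does not allow it: with no landmark distal to the fracture, a contralateral reference alone would not turn the measure into one of limb shortening.

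**What to change.** 1. For femoral offset, replace the paired test with the operated-minus-contralateral difference, both hips read on the same AP pelvis film, and compare that difference between arms. Comparing the operated value between arms with adjustment for the contralateral value is an acceptable alternative. Name the post-operative film used.
2. State that no conclusion will be based on within-arm paired tests.
3. Define baseline, and say which parameter is read on which film and which hip; a short table is enough. It should record that stem angle and canal fill are read on post-operative films only, and that ossification is compared between arms at 12 months.
4. Address the leg length definition separately.

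The cost is mainly wording. The AP pelvis films are already taken, and the exclusion criteria already remove contralateral hips with arthroplasty, past fracture or fracture implants. If the contralateral hip has not been measured, the two blinded readers must add those measurements.
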